3.0 Purpose

The purpose is to evaluate the safety and effectiveness of Mobility+ enteral feeding system via this initial post-market study (510k clearance number K222678) in adults, a subset of the intended use population. This evaluation will be conducted in a prospective, single arm, non-randomized clinical study.

Hypothesis and Objectives

The study hypothesis is that Mobility+ meets its intended use, safely. The objectives are to evaluate the below primary and secondary endpoints, through execution of this protocol:

Endpoint	Detail	How it will be measured
Primary: Safety and Effectiveness of Mobility+	Evaluate participants who have received familiarization training can use device, according to IFU, to allow delivery of liquid nutrition to their feeding tube, in a real-life setting (home), safely (i.e. can execute critical device use tasks to allow feeding, without serious adverse events) and with effectiveness (i.e. using Mobility+ for the majority or all of their feeding sessions i.e. two daily feeds, minimum)	Phone communication and checklist (Appendix8)

Secondary: Usability of Mobility+	Evaluate Participant perspectives on mobility, ease of use and tolerance, with their current feeding system(s) and Mobility+	Participant perspectives surveys: Baseline (Appendix 4) End of study (Appendix 7)
	Evaluate changes in participant Quality of Life (QoL)	QoL survey at baseline (Appendix 5) and QoL question at end of study (Appendix 7)
	Estimate if participants consume similar average volume (and kcals) of feed/day during the study, compared to baseline	Collect descriptive data on estimated average feed volume and kcals consumed at baseline (Appendix 3) and at end of study (Appendix 8)

The outcome will be presented in a study report.

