effect (SAE)	
 a) Death b) Serious deterioration in the health of the subject, users, or other persons as defined by one or more of the following: 
 1) A life-threatening illness or injury, or 2) A permanent impairment of a body structure or a body function including chronic diseases, or 3) In-patient or prolonged hospitalization, or 4) Medical or surgical intervention to prevent life-threatening illness or injury, or permanent impairment to a body structure or a body function, c) Fetal distress, fetal death, a congenital abnormality, or birth defect including physical or mental impairment
Adverse device effect (ADE)	Adverse event related to the use of an investigational medical device.
Serious adverse device effect (SADE)	Adverse device effect that has resulted in any of the consequences characteristic of a serious adverse event
Unanticipated serious adverse device effect (USADE)	
Serious adverse device effect which by its nature, incidence, severity or outcome has not been identified in the current risk assessment
 
Note: Anticipated serious adverse device effect (ASADE) is an effect which by its nature, incidence, severity or outcome has been identified in the risk assessment

Serious public health threat	Serious public health threat, means an event which could result in imminent risk of death, serious deterioration in a person's state of health, or serious illness, that may require prompt remedial action, and that may cause significant morbidity or mortality in humans, or that is unusual or unexpected for the given place and time
Stock-Keeping Unit (SKU)	A Stock-Keeping Unit is a number (and sometimes letters) that is assigned to a product for the purpose of inventory management and ease or tracking

	
Safety and Effectiveness of A Novel Enteral Feeding System: Prospective Study Protocol Page 13 of 49
	
NCT06173063

---	---	---

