8.0 Methods

8.1 General Methodology

The study duration will allow 25 participants to use the Mobility+ system for their feeding sessions over the course of 14 consecutive days, following an initial 7-day period where participants have time to trial and get used to the new system. As determined by the PI, five to seven pre-intervention days (During 'Trial days' 1 to 7), with a minimum of 5, is time to allow participants to become familiar with a new feeding system (i.e., Mobility+) and 14 days (Study Day 1 through Day 14 inclusive) is the time required to effectively assess safety and effectiveness of Mobility+ (as outlined in **Appendix 8**).

The environment is Mayo Clinic Setting at study outset for the clinic visits where participants will be screened, consented, and enrolled. Participants' homes are the setting for the 21-day study duration.

Mobility+ Devices will be built by a process detailed within a Mobility+ Work Instruction, from within a quality management system. The work instruction will be in place at the time of Mobility+ production runs occurring before execution of this protocol.

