8.5 Study Measurements

The study measurements which will be taken are detailed in Table 3 below:

Table 3: Study measurements

Baseline measurements:	
 Demographics (Appendix 3) Average volume and Kcals of feed consumed / day (Appendix 3) Quality of life measure (Appendix 5) Participant perspectives on mobility, ease of use (current system(s)) and feeding intolerance symptoms (Appendix 4)
Trial days	
 Tubing SKU check (Appendix 6)
Interim survey questions (Study Day 7)	
 Tubing SKU check, safety and effectiveness check, compliance and calorie intake check (Appendix 8)
End of study measurements (Study Day 14):	
 Quality of life question (Appendix 7) Participant perspectives on mobility and ease of use of Mobility+ system (Appendix 7) Note of tubing SKU used, safety and effectiveness check, compliance and calorie intake check, General end of study questions (wearing, wellbeing, future use etc.) (Appendix 7)

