Participants will be made aware at enrollment that operators who are licensed to prescribe enteral feeding systems may advise changes to the giving-set tubing SKU they use, throughout the study, should clinical and participant factors necessitate this.

During phone communications in the trial period days, the operator will advise the participant about what, if any, changes to make to the tubing SKU they are using, which will be logged (**Appendix 6**). If necessary, participants will be advised by the operator to move to tubing SKUs which provide faster or slower flow rates as tolerated (See Phone Communication Decision Tree Figure 7), until the participant has their optimum tubing SKU selected by the end of the trial period, for use during the study days. The participant will then ideally continue with the selected tubing SKU for the duration of the study days.

[figure not shown]

Figure 7: Phone Communication Decision Tree

However, on study Day 7 operators will discuss the tubing SKU being used with the participant and advise if any changes need to be made. Any changes made to the SKU being used will be logged by the operator (**Appendix 6**). On study day 14 (at outcome), operators will log the SKU that participants finished the trial with.

Participants will be supplied with devices, tubing SKUs and other consumables necessary, for trial period and study days.

Table 4 and **Figure 8** below summarizes the study schedule and the subsequent text details what occurs at screening and baseline visit, and in the pre-intervention and intervention phases.

Note: Operators will, if applicable, log reports on 1) surveys/phone communications that subjects fail to respond to (including reasons), and 2) participants withdrawn (including reason for withdrawal)

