8.11 Phone Communication

1. Pre-intervention phase – Trial days

Phone communication on **Trial Days 1; 3 and 5**: Participant is contacted by telephone to ensure the participant is becoming familiar with using the device including the most appropriate giving-set tubing SKU. (**Appendix 6**).

2. Intervention phase – Study days

- Phone communication - Study **Day 7**: Participant is contacted by telephone to ensure they are successfully and safely feeding with an appropriate tubing SKU, and check compliance and calorie intake (**Appendix 8**).
- Phone communication -Study **Day 14**: Participant is contacted by telephone to ensure participant is successfully and safely feeding with an appropriate tubing SKU, and check compliance and calorie intake. Operator also evaluates self-perceived wellbeing, mobility, wearing methods, and longer-term device use wishes (**Appendix 8**) Administer participant perspectives outcome survey, including question on QoL (**Appendix 7**)

Note: Regarding disposal – as per IFU, devices are disposed of alongside normal waste.

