		

How strongly do you agree with the following statement? I would like to use the Mobility+ again.

Strongly Agree	Somewhat Agree	Neutral	Somewhat Disagree	Strongly Disagree
				

If you would like to use Mobility+ again, how often would you like to use it?

Every Day	Every Week	Every Month
		

Think about your overall wellbeing if you used Mobility+ for SOME/ALL of your tube feeding needs, in the long term. How would your wellbeing be then, compared to now?

Much Better	Somewhat Better	About the Same	Somewhat Worse	Much Worse
				

Would you pay out of pocket for the Mobility+?

YES	NO
	

How did you choose to wear the Mobility+ system?

- Crossbody bag**
- Handbag**
- Backpack**
- In clothing**
- Clipped onto belt/clothing**
- Other (Detail):**

Appendix 8

Appendix 8 - Phone communication check sheet (Study Day 7 and 14) - (Operator asks the Participant these questions)

Day 7

Day 7			
Questions:	Answers:		
Day 7 Safety & Effectiveness Check			
Are you able to use Mobility+ to successfully and safely provide enteral feeding?	 YES  NO		
Day 7 Compliance & Calorie Intake Check			
Consider your feed intake over the last 3 days (i.e. Study day 4, 5, 6).			
Questions:	Answers:		
What volume of enteral nutrition did you consume on average per day (i.e. over 24 hr)?	Volume Mobility+mls		
How many hours did you typically infuse for, on average/day? hours minutes		
How many feedings did you intend to take using Mobility+ , on average / day?feedings		
How many feedings were you able to take using Mobility+ , on average / day?feedings		
What was the average volume of enteral nutrition that you consumed per feeding with Mobility+?mls		
What time of the day did you provide feedings with Mobility+?	Morning  Afternoon  Evening  Night-time 		
Operator facing question: On average, did the participant take at least two daily feeds with Mobility+? If no, why not?	 YES		
	 NO		
Day 7 Tubing SKU check			
Study Day 7:			
SKU that participant is using:			

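### With the Study Day 7 call made, no form template asks about hospital admissions between the Trial Day 5 and Study Day 7 calls, although the primary endpoint requires absence of SAEs

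*Protocol*

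**What the plan says.** **Endpoint.** In Protocol section 3.0 the safety half of the primary endpoint is that participants "can execute critical device use tasks to allow feeding, without serious adverse events". The stated means of measurement are phone communication and the Appendix 8 checklist. Section 3.0 adds: "The outcome will be presented in a study report".

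**Hospitalisation.** "In-patient or prolonged hospitalization" is one of the SAE criteria in section 7.0, and that section counts adverse events whether or not the device caused them. Section 8.13 ends participation on hospitalisation for any reason, during trial or study days, and cites Appendices 6 and 8.

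**Study Day 7.** For this day Table 3 in section 8.5 lists "Tubing SKU check, safety and effectiveness check, compliance and calorie intake check (Appendix 8"). Section 8.11 describes the call in similar terms: "Participant is contacted by telephone to ensure they are successfully and safely feeding with an appropriate tubing SKU". Neither mentions an admission check. The one safety question on the Appendix 8 Day 7 sheet is "Are you able to use Mobility+ to successfully and safely provide enteral feeding", answered yes or no, and the Day 14 sheet repeats it.

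**Where admission is asked.** Appendix 6 asks at Trial Day 5 about the previous 5 days or the trial period. Appendix 7, used at Study Day 14, asks about the time since the last phone contact.

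**SAP.** SAP section 7.0 reports 17 (100%) for successful and safe feeding as supplemental data, in words close to the self-rating. The SAP gives no SAE count.

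**The concern.** The checklist named for an endpoint that requires absence of SAEs does not ask about SAEs, or about the most easily prompted SAE criterion, admission to hospital. The self-rating concerns the participant's ability to feed safely with the device, so a truthful yes is compatible with a recent admission for another reason.

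Consider a participant admitted on Study Day 2 and discharged before the Day 7 call. On the templates, that person is not asked about admission on Day 7, can answer yes to the feeding question on both calls, and on Day 14 can truthfully report no admission since the last contact. Unless the event becomes known in some other way, it does not reach the SAE records and the section 8.13 rule is not triggered. At stake is how complete the SAE ascertainment behind the safety claim is, and whether a reader takes a self-rating for the SAE result.

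**Working it through.** **Inputs.** The trial period lasts 5 to 7 days (section 8.1: "with a minimum of 5, is time to allow participants to become familiar with a new feeding system") and the study period 14 days. Trial-period calls fall on Trial Days 1, 3 and 5, and study-period calls on Study Days 7 and 14 (section 8.11, Table 4). The two admission questions are those in Appendices 6 and 7.

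**The plan's own figure.** 7 trial days + 14 study days = 21 days, which matches the duration in section 8.1. The shortest permitted trial period gives 5 + 14 = 19 days.

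**Coverage by form, with all calls made.**

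| Call | Form | Admission question | Period covered |
|---|---|---|---|
| Trial Day 5 | Appendix 6 | Yes | Trial Days 1 to 5 |
| Study Day 7 | Appendix 8 | No | None |
| Study Day 14 | Appendices 7 and 8 | Yes, Appendix 7 only | Since the Study Day 7 call |

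**Length of the gap.** Let T be the number of trial days. Uncovered trial days = T − 5. Uncovered study days = 6 if Study Day 7 counts as covered by the Day 14 look-back, or 7 if it does not. Total days = T + 14.

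| T | Uncovered trial days | Gap, Study Day 7 covered | Gap, Study Day 7 not covered |
|---|---|---|---|
| 5 | 0 | 0 + 6 = 6 of 19 (31.6%) | 0 + 7 = 7 of 19 (36.8%) |
| 6 | 1 | 1 + 6 = 7 of 20 (35.0%) | 1 + 7 = 8 of 20 (40.0%) |
| 7 | 2 | 2 + 6 = 8 of 21 (38.1%) | 2 + 7 = 9 of 21 (42.9%) |

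Section 8.1 makes the 14 study days the period for assessing safety. Within them the gap is 6/14 = 42.9% to 7/14 = 50.0%. With a 5-day trial period there is no Trial Day 6, and the gap starts at Study Day 1.

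**If the Day 7 call is missed.** The last contact before Day 14 is then the Trial Day 5 call. The Appendix 7 look-back reaches that far and the gap is zero.

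**After the change.** With the Appendix 7 wording on the Day 7 sheet, the three look-back periods join end to end, and no day before the Day 14 call is uncovered for any T.

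**The case against.** **Other routes exist.** Participants have the operator's phone number (section 8.12). Events learned of by phone or otherwise are assessed (8.13). The PI records AEs and SAEs and reports serious matters within 24 hours (10.0, Appendix 10), and withdrawals are logged with reasons (8.7). The endpoint measure includes the phone contact itself, not just the checklist. This stands: the day counts describe one prompt, not SAE detection as a whole. These routes do, however, depend on someone volunteering or learning of the event.

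**The 8.13 citation may be a slip.** The same section cites Appendix 9 for phone monitoring, where Appendix 8 fits, and section 8.12 cites Appendix 14 for operator training, whose record is Appendix 13. Both are one too high, so the 8 may mean 7. In that case no Day 7 admission item was ever promised, and a reader should not infer a broken commitment. The slip is not certain, since 8.13 cites Appendices 9 and 10 correctly for event assessment. Either way, Appendix 7 is not used on Day 7, so the gap remains.

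**The intake questions might help.** On Day 7 they cover Study Days 4 to 6. If they surfaced every admission on those 3 days, 6 − 3 = 3 to 7 − 3 = 4 study days would remain. They ask about volumes, feeds and times, so this is a generous assumption.

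**Stronger readings that fail.** A reader might infer that an SAE was missed; nothing in the documents shows this. A reader might also infer that an unrecorded admission would lower the 17 (100%) figure. It would not: that row follows the self-rating, to which such a participant could still answer yes, and neither document reports an SAE-based figure.

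**Conclusion.** The point holds as a gap in prompted questioning. When the Study Day 7 call is made, no form template asks about admissions between the Trial Day 5 and Study Day 7 calls. That is 6 to 7 of the 14 study days, plus 0 to 2 trial days. The checklist named for the primary endpoint has no SAE or admission item at all.

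The conclusion assumes that calls were made on schedule and that the forms used matched the appendix templates. Figures 7 and 8, the data-capture forms, the participant information sheet and the study report are not visible, and any of them could add prompts or already give the SAE count. The documents therefore support no statement about how many events, if any, went unrecorded. The 17 (100%) row should not be read as the SAE result, and the SAP does not present it as one. The difference between 19 included participants and the n=17 tables is a separate matter and is not evidence for this point.

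The correction is worth making: it is cheap and bears directly on the primary safety endpoint.

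**What to change.** 1. Reconcile the appendix references in section 8.13 with the forms that carry the admission question.
2. For any further use of the protocol, add the existing Appendix 7 admission question, looking back to the previous call, to the Study Day 7 sheet of Appendix 8.
3. State in the SAP or study report that the safety half of the primary endpoint is derived from SAEs in the AE records, among all participants who used the device. Show that count beside the 17 (100%) self-rating row and label the row as a self-rating.
4. If the data-capture forms matched the templates, state in the report that, for participants whose Day 7 call was made, admissions between the Trial Day 5 and Study Day 7 calls were not prompted.

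The cost is one extra question on a call already scheduled, a few sentences of reporting, and a count from records the PI must already keep. The form change cannot affect data already collected, so for this study only items 1, 3 and 4 apply.

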1.0 Purpose

The purpose of this document is to record the sample size, scoring ratings and statistical methods applied to the Mobility+ Post-Market Clinical Study.

It also captures the supplemental baseline and outcome data recorded during the study.

2.0 Reference Documents

Document Type	Document Description
CLP001	Mobility+ Post-Market Clinical Study Protocol

3.0 Sample size

The aim was to recruit 25 participants, to allow for potential dropouts and obtain data for an ideal minimum of 20 participants. The number of patients who were screened was high, at 548. Of this 548, a high proportion (n= 493, 90%) were excluded as they did not meet the study criteria. Furthermore, 11 declined to take part, 25 did not take part for other reasons (e.g. did not show up to appointment or their clinical plan included intent to taper down enteral nutrition (EN) intake), resulting in 19 being the number of participants included. This was the highest number feasible to include in the time frame of the screening and close to the ideal minimum of 20 participants.

4.0 Scoring ratings

A score was given for each rating from 1 to 5, with 5 being the most positive response.

The scoring systems applied were as outlined below:

Patient perspectives on mobility (using current system vs. Mobility+)	Very easy (5) Easy (4) Neutral (3) Difficult (2) Very difficult (1).
Patient perspectives on ease of use	Strongly agree (5) Somewhat agree (4) Neutral (3) Somewhat disagree (2) Strongly disagree (1).
Participant perspective on Quality of life	Excellent (5) Good (4) Neutral (3) Bad (2) Very bad (1)

An overall score for each measure was calculated and averaged for the cohort.

5.0 Statistical test applied

The statistical test used was a paired T-test with ANOVA. Statistical significance was set at $P < 0.05$. Analyses were performed with IBM SPSS Statistics for Windows, version 29.0.1 (IBM Corp., Armonk, N.Y., USA).

6.0 Supplemental Baseline data gathered

The following supplemental Baseline Data was gathered at patient enrollment (n=17).

Variables	
Diagnosis, n (%)	
Malignancy	13 (76.5)
GI Dysmotility	2 (11.8)
Bariatric Surgery	1 (5.9)
Functional Disorder	1 (5.9)
Occupation, n (%)	
Working/studying	6 (35.3)
Not working/studying	11 (64.7)
Type of Feeding Tube, n (%)	
G-Tube	14 (82.4)
J-Tube	3 (17.6)
Type of Feeding System before study, n (%)	
Infusion Pump	4 (23.5)
Bolus/Syringe	3 (17.6)
Gravity	7 (41.2)
Combination*	3 (17.6)
Daytime or Night-time Feeds n (%)	
Daytime Only	10 (58.8)
Nighttime Only	1 (5.9)
Both Day & Night-time	6 (35.3)

*Combination was Bolus/syringe, Gravity.

7.0 Supplemental Outcome data gathered

The following supplemental Outcome Data was gathered (n=17).

Compliance and Effectiveness (n (%))	
Successfully and safely feed with Mobility+	17 (100)
Achieved use of Mobility+ for minimum 2 daily EN feeds	16 (94.1)

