8.3 Participants

This is a first in human post-market clinical study to evaluate the Mobility+ system, being carried out following market approval (i.e., FDA clearance). 25 participants will be enrolled to ensure data can be obtained for 20 participants (the expected drop-out rate is estimated at ~20%), as this is considered appropriate for a post-market clinical study on a low-risk device and will add meaningful data to device risk management files. If more than 5 participants drop out, re-recruitment will aim to bring the sample size up to 20.

Recruitment will aim to obtain a mix of female and male participants who meet the inclusion criteria. Screening questions will be used by operators during the recruitment process to ensure participants are eligible (See **Appendix 1** and **Appendix 2**).

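### SAP 3.0 sets 19 included against a target of 20 with data, but the tables cover 17; two are unexplained and the joint primary endpoint is not reported

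*SAP*

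**What the plan says.** **Target.** Protocol 8.3 states "25 participants will be enrolled to ensure data can be obtained for 20 participants" and adds that "the expected drop-out rate is estimated at ~20"%. SAP 3.0 repeats the aim: recruit 25 so as to "obtain data for an ideal minimum of 20 participants".

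**Recruitment.** SAP 3.0 starts from 548 screened, removes 493 who did not meet the criteria, 11 who declined and 25 who did not take part for other reasons, "resulting in 19 being the number of participants included". It then describes that number as "close to the ideal minimum of 20 participants".

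**Tables.** SAP 6.0 is introduced by "The following supplemental Baseline Data was gathered at patient enrollment (n=17" and SAP 7.0 by "The following supplemental Outcome Data was gathered (n=17". SAP 7.0 has two rows: successful and safe feeding, 17 (100%), and at least two daily feeds with the device, 16 (94.1%). SAP 1.0 explains the status of these tables: "It also captures the supplemental baseline and outcome data recorded during the study".

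**Primary endpoint.** Protocol 3.0 evaluates participants who have received familiarization training. Success has two parts joined by an emphasised *and*: carrying out the critical device tasks without serious adverse events, and using the device for at least two feeds a day.

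**Records.** Under protocol 8.7 operators log withdrawals and their reasons. Appendix 12 records each participant's training. Protocol 10.0 makes the PI responsible for recording SAEs.

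**The concern.** Two different quantities are compared in SAP 3.0. The target counts people who yield data, and the figure set beside it counts people included. A reader of SAP 3.0 alone would think the study fell one short; the tables show three.

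Neither document says why the other two are absent. People who did not attend had already been removed among the 25, so that group does not explain them. They are missing even from a baseline table labelled as gathered at enrolment.

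This matters because the primary endpoint amounts to a proportion, and its value depends on who is in the denominator. The protocol names the people to be evaluated (those trained), but the SAP does not say whether the 17 are all of them. The joint endpoint also has no row of its own. The row closest to its safety part has wording that matches one self-rated question in Appendix 8, and no SAE count stands beside it. SAP 5.0 names only a paired t-test with ANOVA, which suits the scored surveys and does not describe how the primary proportion is to be estimated.

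**Working it through.** **1. Reproduce the plan's figures.**
- Included (SAP 3.0): 548 − 493 − 11 − 25 = 19. Reproduced; 493/548 = 90.0% also agrees.
- Planned enrolment (protocol 8.3): 20 / (1 − 0.20) = 25. Reproduced.
- Table percentages: 16/17 = 94.1% and 13/17 = 76.5% match the SAP. On 19 they would be 84.2% and 68.4%. Every percentage in SAP 6.0 and 7.0 fits 17, so the denominator is not a typing slip.

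**2. Shortfall against the target of 20 with data.**
- As SAP 3.0 compares it: 20 − 19 = 1, and 1/20 = 5%.
- Like for like: 20 − 17 = 3, and 3/20 = 15%.

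**3. Unaccounted participants.**
- 19 − 17 = 2, and 2/19 = 10.5%.
- Planned dropout applied to 19: 0.20 × 19 = 3.8, so about 15 with data would have been expected. The 17 observed is better than planned.

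**4. Joint endpoint on the 17.**
- If the two rows are taken as the whole endpoint, the joint count is at least 17 + 16 − 17 = 16 and at most min(17, 16) = 16, so exactly 16.
- Any SAE among those 16, or any critical task not carried out, would lower it. Neither is tabulated, so 16/17 is a ceiling.
- 16/17 = 94.1%, exact (Clopper-Pearson) 95% CI 71.3 to 99.9.

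**5. Joint endpoint on the protocol's population.** How many of the 19 were trained is not stated, so each case below is an assumption. All are ceilings, for the reason in step 4.

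| Trained | Other trained participants who succeed | Ceiling | Exact 95% CI |
|---|---|---|---|
| 19 | none of 2 | 16/19 = 84.2% | 60.4 to 96.6 |
| 19 | 1 of 2 | 17/19 = 89.5% | 66.9 to 98.7 |
| 19 | 2 of 2 | 18/19 = 94.7% | 74.0 to 99.9 |
| 18 | 0 of 1 | 16/18 = 88.9% | 65.3 to 98.6 |
| 18 | 1 of 1 | 17/18 = 94.4% | 72.7 to 99.9 |
| 17 | – | 16/17 = 94.1% | 71.3 to 99.9 |

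**The case against.** The strongest reply has five parts.

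- *The tables are supplemental and the results belong in the study report* (protocol 3.0). Participant flow and the SAE count may be there. This stands as a limit: the point concerns what the protocol and SAP show. But neither document directs the reader to a participant account, and the comparison with 20 is in the SAP itself.
- *A population is stated.* Correct: protocol 3.0 names trained participants, so it would be wrong to say that nobody is defined. What is missing is the link between that population and the 17.
- *The two may have left before training.* Protocol 8.10 lists enrolment before the questionnaire that confirms eligibility, with baseline measures and training later in the visit. Someone could leave in between, which would fit n=17 in both tables. If that happened to both, the figures on 17 stand. It should then be stated.
- *A joint row adds little.* For the two printed items this is right, since the joint count is 16. It does not supply the SAE component.
- *No threshold or test is attached, so n (%) is enough.* This limits the consequence. With so few participants, an interval still tells the reader how little the percentage pins down.

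A time point is not wholly absent either: the protocol uses the word outcome for Study Day 14, which is the natural reading of SAP 7.0.

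A reader might infer that the two were failures left out of the table, perhaps after a hospital admission, which ends participation under protocol 8.13. The documents do not show this, nor do they show that the 17 are completers. A reader might also take 94.1% as a cap whatever the denominator. It is not: on 19 the ceiling could reach 94.7%.

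**Conclusion.** The point holds as a reporting fault that should be fixed. SAP 3.0 makes the wrong comparison, and the right one is 17 against 20. Two of 19 are unexplained. The joint primary endpoint is not reported as defined, because the SAE component is missing and the denominator is not tied to trained participants.

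On the 17 the joint result is at most 94.1%. Over the possible numbers trained, the ceiling runs from 84.2% to 94.7%. This assumes that the 16 recorded as meeting the two-feed criterion stand, that those 16 had no SAE and carried out the critical tasks, and that 17 to 19 participants were trained.

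The amount of loss is not the fault, and the SAP does not claim a joint result of 17/17. With no stated threshold, what changes is the reported figure and its precision, not a pass/fail decision.

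**What to change.** Label all of the following as post hoc, because the SAP already contains results.

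1. Restate SAP 3.0 as 19 included and 17 with data, against a target of 20 with data.
2. Account for the two others from the protocol 8.7 withdrawal log and the Appendix 12 training records.
3. Report the joint endpoint per participant on all who received familiarization training, with an exact 95% CI and the SAE count from the PI's record.
4. Count a participant with an SAE as a non-success, as the protocol's definition requires.
5. For trained participants without outcome data, show worst-case and best-case bounds and no single imputed value.
6. Keep n=17 as a separate line, labelled participants with outcome data.
7. State that the SAP 7.0 rows refer to Study Day 14, if that is so.

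If the study report already gives these figures, a citation to it in the SAP covers items 2 to 5.

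The cost is a few sentences of SAP wording and a small re-analysis of data and logs that the protocol already requires. The stated rate may become less favourable. No rule on conduct or clinical management is touched.
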